6.5. DEFINITION OF REGIONS

Not applicable.

6.6. WINDOWS FOR TIME POINTS

For each visit, a window of time for analysis endpoints may need to be defined:

- Week 4 (V3) may be defined as between 25 and 31 days.
- Week 12 (V4) may be defined as between 77 and 91 days.
- Week 24 (V5) may be defined as between 161 and 175 days.
- Visit LTE1 (W36) may be defined as between 245 and 259 days.
- Visit LTE2 (W48) may be defined as between 329 and 343 days.
- Premature withdrawal visit will be allocated to a study visit according to the delay between baseline and premature withdrawal, if and only if this study visit has not been attended yet. For example, if a patient withdrew after V3 and time to withdrawal between 77 and 91 days, then premature withdrawal data collected will be considered as V4 data. If time to withdrawal is below 77 days, data will not be considered in the analysis.

See Graphical study design (Figure 1) in the Section [1.1](#).

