## 10 STUDY PROCEDURES

### 10.1 VISIT SCHEDULE

The visit schedule consists of the following visits:

- Screening Visit (V1). This visit will be performed over a 28-day period prior to Visit 2. No IMP will be administered during this period
- 6-month core period (D1 to Week 24). Four visits are planned after screening: V2 (baseline, first sarilumab injection at D1), V3 (Week 4 ± 3 days), V4 (Week 12 ± 7 days), and V5 (Week 24 ± 7 days)
- LTE period for patients who will complete the 6-month core period: V LTE1 (Week 36 ± 7 days) and V LTE2 (Week 48 ± 7 days) or until the commercial availability of sarilumab in France
- Post-treatment observations (V6). One visit is planned between two and four weeks after the last IMP administration.

In case of premature withdrawal, the patient should perform a specific visit as soon as possible after the last IMP dose administration.

The visits' schedule is detailed in section 1.2. If a visit date is changed, the next visit should take place according to the original schedule.

The patients will be requested to complete PROs questionnaires during their clinical visits (at each visit over the 6-month core period and at premature withdrawal if applicable), before any other assessments. Over the treatment period, when IMP administration is performed at the time of an assessment visit, the injection should be done after all study assessments.

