#### **10.1.5 Assessments at early termination visit**

If a patient withdraws from the study at any time point, an early withdrawal visit must be completed as soon as possible after the last dose of study drug. If a patient withdraws at a visit, this visit should proceed as an early withdrawal visit. In this case, only the withdrawal visit assessments should be conducted.

The investigator or designee will:

- Record body weight and waist circumference.
- A general physical examination should be performed.
- Record vital signs.
- Record the size of the largest rheumatoid nodule (if applicable).
- Ask the patient to complete the following self-assessments: RAID, HADS, MATHyS, FACIT-Fatigue, HAQ-DI, duration of morning stiffness, IPAQ, and patient global assessment of disease activity (VAS)
- For female patients of child-bearing potential performed a urine pregnancy test. If the urine test is positive it must be confirmed by a serum pregnancy test.
- Record the results of hematology, serum chemistry, serum iron, 25OHD, and fasting lipids results.
- Complete the ACR core set assessments including: ESR, DAS28-ESR, CDAI, and joint counts (TJC and SJC on 28 joints).
- Review concomitant medications
- Assess IMP compliance / review patient diary
- Inquire about and record any adverse events/SAEs.
- Record the reason(s) for early termination.

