5.1.2. Primary endpoint (6-month core period)

Primary endpoint is the change in RAID score from baseline to W24. The RAID score ranging from 0 (best) to 10 (worst).

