6.4. MISSING DATA

For the primary endpoint, in case of treatment discontinuation due to lack of efficacy (as defined in Protocol Version 2 section 11.4.2.1) or adverse event (except for AEs due to NSAID), the last available endpoint before the considered event will be taken in account (for [RAID](#) score for primary endpoint and for all other secondary endpoints). For all other cases, missing data will not be replaced.

MISSING OR INCOMPLETE DATES

For all dates (except adverse events and concomitant treatments):

- If only day is missing, it will be replaced by '15'
- If day and month are missing, day will be replaced by 1 and month will be replaced by July '7'
- In case of missing year or complete missing date, no replacement will be performed

For dates relative to adverse events (AE) and concomitant treatments, if a date is completely or partially missing, date will not be replaced but:

- If day is missing and start date/end date of AE/treatment occurred before or the same month as the end of study, AE/treatment will be considered as "treatment-emergent" by default.
- If day and month are missing and start date/end date of AE/treatment occurred the same year as the end of study, AE/treatment will be considered as "treatment-emergent" by default.
- In case of missing year or complete missing date, start date/end date of AE/treatment will be considered as "treatment-emergent" by default.

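### RAID collected at early withdrawal is used or dropped by calendar day, and for some leavers an older RAID then stands for Week 24

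*SAP*

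**What the plan says.** - **Endpoint.** SAP 5.1.2: "Primary endpoint is the change in RAID score from baseline to W24". SAP 5.3.2.2 reports the mean change with a two-sided 95% CI and also fits a repeated-measures mixed model.
- **Collection.** Protocol 10.1.5 states that "an early withdrawal visit must be completed as soon as possible after the last dose of study drug", and RAID is among its assessments. Protocol 10.1 likewise schedules the questionnaires "at each visit over the 6-month core period and at premature withdrawal if applicable".
- **Windows.** SAP 6.6 gives the first window in tentative terms: "Week 4 (V3) may be defined as between 25 and 31 days". It sets the other two core windows in the same form, at days 77-91 for V4 and days 161-175 for V5. Withdrawal data go to the visit whose window matches the delay since baseline, and only if the patient has not already had that visit. For a patient who leaves after V3, data from days 77-91 become V4 data. The example then ends: "If time to withdrawal is below 77 days, data will not be considered in the analysis".
- **Carry-forward.** Under SAP 6.4, when treatment is discontinued for lack of efficacy or an adverse event (NSAID-related events excepted), "the last available endpoint before the considered event will be taken in account". This covers the secondary endpoints as well. In every other case a missing value stays missing. Protocol 11.4.2.1 also takes the last value preceding the event.

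**The concern.** The withdrawal RAID is mandatory, it measures the primary endpoint, and it is the observation closest to the reason for leaving. Whether it is used depends on the day the patient happens to attend. After V3, the same questionnaire counts as V4 data on day 77 and is ignored on day 76. Neither the reason for leaving nor the treatment status enters the rule.

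The two SAP sections also do not fit together. A lack-of-efficacy leaver seen on days 161-175, before V5, has a V5 value under 6.6 but a carried earlier value under 6.4.

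At stake is the mean change in a single-arm study. If patients who leave for lack of efficacy are represented by a RAID taken before they deteriorated, the mean improvement at Week 24 would look too large, and no control arm would reveal it.

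**Working it through.** **1. The plan's own figures.** SAP 1.4 gives SD 2.5 and 122 evaluable patients. The half-width is 1.96 × 2.5 / √122 = 0.44, as stated. The protocol synopsis gives 112 evaluable (140 × 0.80 = 112), for which 1.96 × 2.5 / √112 = 0.46. The windows follow from the flow chart tolerances: 28 ± 3 gives days 25-31, 84 ± 7 gives 77-91, and 168 ± 7 gives 161-175.

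**2. How many withdrawal days are usable.**
- The core windows cover 7 + 15 + 15 = 37 of days 1-175 (21%).
- On days 1-160, 7 + 15 = 22 days are inside a window and 138 (86%) are outside.
- On days 32-160, between the W4 and W24 windows, 114 of 129 days (88%) are outside: days 32-76 (45 days) and 92-160 (69 days).
- The requirement that the visit has not yet taken place narrows this further. With visits on days 28, 84 and 168, the usable days are 25-27, 77-83 and 161-167. That is 3 + 7 + 7 = 17 of days 1-167 (10%).
- If the day-77 sentence is read as applying to every patient, it also removes the W4 window and leaves 15 + 15 = 30 of 175 days (17%). That contradicts the W4 window itself.

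**3. How old the carried value can be.** With V3 on day 28 and withdrawal on day 76, the carried RAID is 76 - 28 = 48 days older than the unused one. With V4 on day 84 and withdrawal on day 160, it is 160 - 84 = 76 days older. Before V3 the only earlier RAID is baseline, so the carried change is 0.

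**4. Possible effect on the mean.** Shift = (share of patients whose withdrawal RAID is replaced by an older one) × (withdrawal RAID minus carried RAID). Higher RAID is worse, so a positive difference overstates improvement and a negative one understates it. The documents give neither quantity; both are assumed here. The formula applies to the simple mean.

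| Share | 0.5 points | 1 point | 2 points | 3 points |
|---|---|---|---|---|
| 5% | 0.03 | 0.05 | 0.10 | 0.15 |
| 10% | 0.05 | 0.10 | 0.20 | 0.30 |
| 20% | 0.10 | 0.20 | 0.40 | 0.60 |

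Only the last cell exceeds the half-width of 0.44-0.46.

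**5. One worked case.** Assume 10% of patients leave for lack of efficacy, evenly over days 1-160, with RAID 2 points worse than at the last visit. Counting only the window gaps after V3, the shift is 0.10 × 114/160 × 2 = 0.14 points. Including the 24 days before V3 would give 0.10 × 138/160 × 2 = 0.17, but that is not justified, because the carried change there is zero.

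**The case against.** The case on the other side has real force.

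- **The windows are not the only cause.** SAP 6.4 and Protocol 11.4.2.1 both ask for a value preceding the event, and the withdrawal visit follows the last dose. Where the event is the discontinuation, this wording keeps the withdrawal RAID out whatever the windows are. This stands: changing 6.6 alone would not be enough, and using the value departs from the protocol.
- **The affected group is narrower than all who stop treatment.** Protocol 10.3.4 and 10.3.5 keep such patients in follow-up where possible; the withdrawal visit is for those who leave the study. Leavers for other reasons get no carried value. They drop out of the simple Week 24 mean, and the mixed model uses only their earlier visits. This stands.
- **The text is tentative.** The windows are worded as possibilities, the day-77 sentence closes an example, and no sentence addresses days 92-160. Non-use on those days is an inference from the allocation rule. This stands, although a rule that feeds the primary endpoint should not be left tentative.

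A reader might also infer three stronger points that the documents do not support:

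- That a scheduled Week 24 visit on day 176 is deleted. No stated rule deletes scheduled visits outside a window.
- That the trial expects to run short of data. The 20% non-evaluable are planned for, and 112 evaluable patients still meet the 0.5 target.
- That the extra day in the Appendix A time-to-withdrawal formula misassigns visits. SAP 5.3.1 presents that variable under disposition, and 6.6 does not say it uses it. The day count merely needs stating.

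**Conclusion.** The point holds as a gap in the plan that is cheap to close. Collected primary-endpoint data are used or left out by calendar day, and for patients who discontinue for lack of efficacy or an adverse event and leave the study, an older RAID can stand for Week 24. The day counts follow directly from the stated windows; the 48- and 76-day figures assume visits on nominal days.

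It is tempting to conclude that the primary result will be biased in favour of sarilumab. The documents do not establish that. Overstatement is plausible for lack-of-efficacy leavers after V3. Before V3 the carried value is baseline, which does not favour the drug, and for adverse-event leavers the direction is unknown. Over the assumed ranges the shift is 0.03-0.60 points, mostly below the half-width.

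**What to change.** 1. In SAP 6.4, state that a RAID collected at the early-withdrawal visit counts as the last available value when a value is carried forward for lack of efficacy or an adverse event. Record this in SAP 1.6 as a change from Protocol 11.4.2.1.
2. In SAP 6.6, replace the gapped windows for the withdrawal visit with contiguous ones on one stated day count. Midpoint cuts (W4 days 1-56, W12 days 57-126, W24 from day 127 to the end of the core period) are one convention. State also what happens when the matching visit was already held. Otherwise, with V3 on day 28 and V4 on day 84, withdrawals on days 29-56 and 85-126 (28 + 42 = 70 of 160 days, 44%) would still be unallocated. No collected withdrawal RAID should be dropped by calendar day alone.
3. Report the carry-forward as now written as a sensitivity analysis.

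The cost is SAP wording, a recorded departure from the protocol, and programming; the data are already collected. The downside is that some values lie further from the nominal date: with midpoint cuts, a day-127 value labelled Week 24 is 168 - 127 = 41 days early.

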6.7. STATISTICAL TECHNICAL ISSUES

Not applicable.

7. ANALYSIS OF BASELINE DATA

Analysis of baseline data details have been presented in a separate document (SANOFI - SARIPRO- Statistical Analysis Plan - INTERIM ANALYSIS Version 2.0 20190611).

8. SOFTWARE DOCUMENTATION

8.1. HARDWARE

The statistical analysis will be performed using Windows 7 professional and a 64-bit operating system.

8.2. SOFTWARE

All tables, listings and figures will be produced and statistical analysis performed using SAS® version 9.3 or above. All outputs will be edited in Microsoft Word Format.

8.3. VALIDATION OF PROGRAMS

Validations will be done according to the procedure of the CRO ITEC Services.

The program reviewer is responsible for reviewing each project program and output provided to the sponsor. Program logs are reviewed for logical, syntax and fatal errors. The review in SAS® includes, but is not limited to, all ERRORS, WARNINGS, BY-VALUE merge messages, NOTES, and UNINITIALIZED variables. Program logs are also reviewed for accurate and consistent variable and observation counts following each procedure and data step.

The reviewing statistician is responsible for checking and reviewing the work produced using whatever method he/she feels is appropriate (e.g., SAS® code review, hand calculation, etc.) to reassure of the quality of the output.

Outputs are reviewed for typographical errors, misspellings and nonsensical values or results and to check the consistency with the statistical and analysis plan. Outputs are cross-checked against each other for accuracy and consistency. For statistical tables, listings, appendix listings, and figures, this procedure includes comparison of subject group numbers, counts of subjects at each observation point, and consistency of results for variables between outputs.

Findings of the quality control reviews are communicated to the party responsible for making necessary changes. The programs will be retested after modifications.

After final review, and when no further changes are required to produce the deliverable, the program reviewer and the statistician in charge of the study need to complete and sign a validation checklist, to indicate that they have successfully performed all of their responsibilities.

Copies of the internal quality control forms produced for the validation process and the sign-off forms will be provided to the sponsor to support the validation if asked.

8.4. RESTITUTION OF THE PROGRAMS

All programs (including Macros and SAS® analysis datasets) producing the tables, listings and statistical output along with associated logs should be given to the sponsor when the tables, listings, figures and statistical analysis has been finalised.

APPENDIX A: DERIVED DATA

The derived data are variables which are calculated from the raw data in the CRF/eCRF and not included in the database (e.g.: AUC, total score, duration, summary value from repeated observations, study exposure, study drug exposure, study drug cumulative dose, etc.).

The formula used for derived data should be provided and examples may be necessary to clarify the calculation. The strategy for missing data must be specified in the calculation of derived data (e.g.: the minimum number of observations required to calculate an average score, handling incomplete dates).

All references used to calculate the derived data should be mentioned below.

The following derived data will be calculated and included in the listings:

(1) SUBGROUPS DECISION

Treatment started before screening visit and ongoing at screening visit	Prescribed treatment at baseline
csDMARDs	Sarilumab + csDMARDs
Biological therapy	Sarilumab + csDMARDs
csDMARDs or biological therapy	Sarilumab in monotherapy

(2) DAS28-ESR

$DAS28-ESR = 0.56 \times \sqrt{TJC28} + 0.28 \times \sqrt{SJC28} + \ln(ESR) + 0.014 \times PtGA$ (in mm)

Where:

- ln is the natural logarithm
- SJC is the swollen joints
- TJC is the tender joints
- PtGA is the patient's global assessment of disease activity (using a 100 mm VAS)
- ESR is the erythrocyte sedimentation rate (mm/h)

(3) CDAI

$CDAI = TJC28 + SJC28 + PtGA(\text{in cm}) + PhGA(\text{in cm})$

Where:

- SJC is the swollen joints
- TJC is the tender joints
- PhGA is the physician's global assessment of disease activity (using a 100 mm VAS)
- PtGA is the patient's global assessment of disease activity (using a 100 mm VAS)

(4) BMI

BMI (kg/m²) will be derived as $\text{Weight (kg)} / [\text{Height (cm)} / 100]^2$ and rounded to the nearest decimal.

(5) Time between baseline and initial diagnosis (years)

Time between baseline and initial diagnosis in years will be calculated as $(\text{initial diagnosis date} - \text{baseline visit date} + 1) / 365.25$.

(6) Changes from baseline (V2)

Absolute variation (points) from baseline will be calculated as a difference from baseline (e.g. assessment at the visit – assessment at baseline).

Relative variation (%) from baseline will be calculated as: $((\text{assessment at the visit} - \text{assessment at baseline}) / \text{assessment at baseline}) * 100$.

If necessary, evolution will be presented according to decision tables from Appendix B.

(7) Duration of IMP exposure (week)

The duration of IMP exposure is defined as follows: $(\text{last dose date} - \text{first dose date} + 14 \text{ days}) / 7$ regardless of unplanned intermittent discontinuations.

(8) Enrollment duration (months)

Enrollment duration (months) will be calculated as: $((\text{date of last patient last visit} - \text{date of first patient first visit}) + 1) / 30.4375$.

(9) Follow-up duration (weeks)

Follow-up duration in weeks will be calculated as: $((\text{date of last contact with the patient} - \text{date of baseline}) + 1) / 7$.

(10) Time between baseline and premature withdrawal (weeks)

Time between baseline and premature withdrawal in weeks will be calculated as $((\text{withdrawal date} - \text{baseline visit date}) + 1) / 7$.

(11) Time between measures of the rheumatoid nodule (months)

Time between measures of the rheumatoid nodule (months) will be calculated as: $(\text{date of the last measure of the rheumatoid nodule} - \text{date of screening}) + 1) / 30.4375$.

(12) RAID

The RAID is calculated based on 7 Numerical rating scales (NRS) questions (see Appendix C). Each NRS is assessed as a number between 0 and 10. The 7 NRS correspond to pain, function, fatigue, sleep, emotional well-being, physical well-being, and coping/self-efficacy.

Calculation: RAID final value = $(\text{pain NRS value (range 0-10)} \times 0.21) + (\text{function NRS value (range 0-10)} \times 0.16) + (\text{fatigue NRS value (range 0-10)} \times 0.15) + (\text{phys well being NRS value (range 0- 10)} \times 0.12) + (\text{sleep NRS value (range 0-10)} \times 0.12) + (\text{emotional well being NRS value (range 0-10)} \times 0.12) + (\text{coping NRS value (range 0-10)} \times 0.12)$.

Thus, the range of the final RAID value is 0-10 where higher figures indicate worse status. Missing data imputation: If one of the 7 NRS values composing the RAID is missing, the imputation is as follows:

- a. calculate the mean value of the 6 other (non-missing) NRS (range, 0-10)
- b. impute this value for the missing NRS
- c. Then, calculate the RAID as explained above. If 2 or more of the NRS are missing, the RAID is considered as missing value (no imputation).

See: http://pitie-salpetriere.aphp.fr/psaid/raid_psaidd_quest_home.php

(13) **Hospital Depression Scale (issue from HADS)**

Total score of depression is the sum of tick boxes of columns D (see Appendix D). The range of the total score of depression value is 0-21.

(14) **Hospital Anxiety Scale (issue from HADS)**

Total score of anxiety is the sum of tick boxes of columns A (see Appendix D). The range of the total score of anxiety value is 0-21.

(15) **Multidimensional Assessment of Thymic States (MATHys):**

The MATHys is a visual analog scale consisting of 20 items varying from 0 to 10 (see Appendix H). These items corresponded to five dimensions: emotional, cognition, psychomotor function, motivation and sensory perception.

Total score is the sum of the 20 items. The measure is the number of centimetres from the left hand anchor. Items measured from 0 to 10 are: 1; 2; 3; 4; 11; 12; 13; 14; 15; 16; 19; 20 and items measured from 10 to 0 are : 5; 6; 7; 8; 9; 10; 17; 18. A score of 0 corresponds to inhibition of the state evaluated by the item. A score of 5 indicates no change from the patient's usual state and a score of 10 corresponds to excitation for the evaluated state. An overall score of between 0 and 200 is thus obtained. This scale is not devoted to make a diagnosis of mood state but allow to determine the general level of inhibition/activation processes (lower scores indicate general inhibition and higher scores indicate general excitation).

The subscore for **emotional** is obtained by the sum of items: 3; 7; 10; 18. This range is 0 (hyporeactive)-40 (hyperreactive).

The subscore for **cognition** is obtained by the sum of items: 5; 9; 12; 14. This range is 0 (Retardation)-40 (Acceleration).

The subscore for **psychomotor function** is obtained by the sum of items: 2; 11; 19. This range is 0 (Retardation)-30 (Acceleration).

The subscore for **motivation** is obtained by the sum of items: 4; 15; 16; 17. This range is 0 (Decrease)-40 (Increase).

The subscore for **sensory perception** is obtained by the sum of items: 1; 6; 8; 13; 20. This range is 0 (Decrease)-50 (Increase).

See: Chantal Henry, Katia M'Bailara, Flavie Mathieu, Rollon Poinot, Bruno Falissard Construction and validation of a dimensional scale exploring mood disorders: MATHys (Multidimensional Assessment of Thymic States). BMC Psychiatry. 2008; 8: 82.

(16) **Functional Assessment of Chronic Illness Therapy – Fatigue (FACIT-F) per item and total score**

The FACIT measurement system is a comprehensive compilation of questions that measure health related QOL in patients with chronic illnesses. The FACIT-F includes the 13 items.

FACIT-F score is the sum of items, this range is 0 to 52. High FACIT-F scores represent less fatigue.

See: CELLA, D, YOUNT, S, SORENSEN, M, CHARTASH, E, SENGUPTA, N ET GROBER, J. Validation of the Functional Assessment of Chronic Illness Therapy Fatigue Scale relative to other instrumentation in patients with rheumatoid arthritis. *J Rheumatol.* 2005; 32: 811-9.

(17) **The Health Assessment Questionnaire - Disability Index (HAQ-DI)**

There are 8 sections: dressing, arising, eating, walking, hygiene, reach, grip, and activities. There are 2 or 3 questions for each section. Scoring within each section is from 0 (without any difficulty) to 3 (unable to do). For each section the score given to that section is the worst score within the section, i.e. if one question is scored 1 and another 2, then the score for the section is 2. In addition, if an aide or device is used or if help is required from another individual, then the minimum score for that section is 2. If the section score is already 2 or more then no modification is made.

The 8 scores of the 8 sections are summed and divided by 8. The result is the disability index. In the event that one section is not completed by a subject then the summed score would be divided by 7. In the event that two section is not completed by a subject then the summed score would be divided by 6 etc. The score range is 0 to 3.

See: Bruce, Bonnie, et James F Fries. « The Stanford Health Assessment Questionnaire: Dimensions and Practical Applications ». *Health and Quality of Life Outcomes* 1, n° 1 (2003): 20. <https://doi.org/10.1186/1477-7525-1-20>.

(18) **International Physical Activity Questionnaire (IPAQ)**

IPAQ assesses physical activity undertaken across a comprehensive set of domains including: leisure time physical activity, domestic and gardening (yard) activities, work-related physical activity and transport-related physical activity.

Results can be reported in categories (low activity levels, moderate activity levels or high activity levels) or as a continuous variable (MET minutes a week). MET minutes represent the amount of energy expended carrying out physical activity. A MET is a multiple of your estimated resting energy expenditure. One MET is what you expend when you are at rest. To get a continuous variable score from the IPAQ (MET minutes a week) we will consider walking to be 3.3 METS, moderate physical activity to be 4 METS and vigorous physical activity to be 8 METS.

Walking MET-minutes/week = 3.3 * walking minutes * walking days

Moderate MET-minutes/week = 4.0 * moderate-intensity activity minutes * moderate days

Vigorous MET-minutes/week = 8.0 * vigorous-intensity activity minutes * vigorous-intensity days

Total physical activity MET-minutes/week = sum of Walking + Moderate + Vigorous METminutes/week scores.

If 'don't know' or 'refused' or data are missing for time or days then that case is removed from analysis.

The items in the short IPAQ form were structured to provide separate scores on walking, moderate-intensity and vigorous-intensity activity. Computation of the total score for the short form requires summation of the duration (in minutes) and frequency (days) of walking, moderate-intensity and vigorous-intensity activities. Domain specific estimates cannot be estimated. Below, physical activity categories are defined:

- Category 1 Low

This is the lowest level of physical activity. Those individuals who not meet criteria for Categories 2 or 3 are considered to have a 'low' physical activity level.

- Category 2 Moderate

The pattern of activity to be classified as 'moderate' is either of the following criteria:

- a) 3 or more days of vigorous-intensity activity of at least 20 minutes per day

OR

- b) 5 or more days of moderate-intensity activity and/or walking of at least 30 minutes per day

OR

- c) 5 or more days of any combination of walking, moderate-intensity or vigorous intensity activities achieving a minimum Total physical activity of at least 600 MET-minutes/week.

Individuals meeting at least one of the above criteria would be defined as accumulating a minimum level of activity and therefore be classified as 'moderate'.

- Category 3 High

A separate category labelled 'high' can be computed to describe higher levels of participation. The two criteria for classification as 'high' are:

- a) vigorous-intensity activity on at least 3 days achieving a minimum Total physical activity of at least 1500 MET-minutes/week

OR

- b) 7 or more days of any combination of walking, moderate-intensity or vigorous-intensity activities achieving a minimum Total physical activity of at least 3000 MET-minutes/week.

Rules to handle inconsistencies: if any inconsistency is detected (for example, an activity 11 days per week, an activity ticked 'No activity' but a time activity completed...), the data will be considered as missing.

See: Guidelines of IPAQ (2005)

(19) **Conversion method for laboratory tests**

a) Lipid panel:

$$\text{Value (mmol/L)} = 5.5 \times \text{Value (g/L)}$$

b) Hematology:

$$\text{Value (}\times 10^{12}/\text{L)} = 1000 \times \text{Value (}\times 10^9/\text{L)}$$

$$\text{Value (g/L)} = 0.1 \times \text{Value (g/dL)}$$

(20) **Normal ranges for laboratory tests (hematology)**

	Man	Women	RANGE
Erythrocytes	4,6 à 6,2 millions/mm ³	4,2 -5,4	<4 et >6
Hemoglobin	13.5 – 17 g/dl	12 – 15,5 g/dl	< 12 et > 18
White Blood Cells	3.5 – 10x10 ⁹ /L		<3.5 et > 10x10 ⁹ /L
Neutrophils	3000 – 5800 x10 ⁶ /L		<3000 et >6000 x10 ⁶ /L
Lymphocytes	1500-3000 x10 ⁶ /L		<1500 et >3000 x10 ⁶ /L
Monocytes	300-500 x10 ⁶ /L		<300 et >500 x10 ⁶ /L
Eosinophils	50-250 x10 ⁶ /L		<50 et 250 x10 ⁶ /L
Basophils	15- 50 x10 ⁶ /L		<15 et >50 x10 ⁶ /L
Platelets	150 000 -400 000		<150 000 et > 400 000

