#### **9.2.1.2 Values at each assessment visit and changes from baseline for ESR, DAS28-ESR, CDAI, and joint counts (TJC, SJC)**

At each visit, all the efficacy parameters will be assessed.

The **erythrocyte sedimentation rate (ESR)** is measured in mm/hr. This laboratory test will be performed in a local medical laboratory.

The DAS28 is a combined index for measuring disease activity in RA. The index includes the assessment of 28 joints for swelling and tenderness, acute phase response (ESR or CRP), and general health status. For this study, ESR will be used to calculate the DAS28 score. The index is calculated using the following formula:

$$\mathbf{DAS28-ESR} = 0.56 \times \sqrt{(TJC28)} + 0.28 \times \sqrt{(SJC28)} + 0.70 \times \ln(ESR) + 0.014 \times PtGA$$

where **TJC28** is the tender joint count on 28 joints, **SJC28** is the swollen joint count on 28 joints,  $\ln$  is the natural log, ESR is the erythrocyte sedimentation rate (mm/hour), i.e., patient's global assessment of disease activity (PtGA using a 100 mm VAS). The 28 joints to be assessed are detailed in Appendix B.

The DAS28 scale ranges from 0 to 10, where higher scores represent higher disease activity.

The **CDAI** is a combined index for measuring disease activity in RA that does not include a laboratory test. It is calculated as follows:

$$\text{CDAI} = \text{TJC28} + \text{SJC28} + \text{PtGA (in cm)} + \text{PhGA (in cm)}$$

where TJC28 is the tender joint count on 28 joints, SJC28 is the swollen joint count on 28 joints, PtGA is patient's global assessment of disease activity (100mm VAS), and PhGA is the physician's global assessment of disease activity (100mm VAS). The 28 joints to be assessed are detailed in Appendix B.

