### **9.2.1.3 DAS28-ESR Low Disease Activity (LDA) and remission, CDAI LDA and remission, at W12 and W24**

A DAS28-ESR score of <2.6 represents clinical remission and a score of  $\leq 3.2$  represents low disease activity.

A CDAI score of  $\leq 2.8$  represents clinical remission and a score of  $\leq 10.0$  represents low disease activity.

For both indexes, clinical remission is included in low disease activity.

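### The SAP's DAS28-ESR formula omits the 0.70 weight on ln(ESR), which inflates scores and would understate DAS28 remission and low-disease-activity rates

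*SAP*

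**What the plan says.** Protocol 9.2.1.2 defines DAS28-ESR as a weighted sum of four components: 0.56 on the square root of the tender joint count, 0.28 on the square root of the swollen joint count, then "0.70 \times \ln(ESR) + 0.014 \times PtGA". It adds: "The DAS28 scale ranges from 0 to 10, where higher scores represent higher disease activity". Protocol 9.2.1.3 sets the cut-offs for that score. "A DAS28-ESR score of <2.6 represents clinical remission", and a score of 3.2 or less is low disease activity (LDA).

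SAP Appendix A, item (2), keeps 0.56, 0.28 and 0.014, but its last two terms are "\ln(ESR) + 0.014 \times PtGA$ (in mm", preceded only by a plus sign. The definitions beneath supply no weight: "ln is the natural logarithm" and "ESR is the erythrocyte sedimentation rate (mm/h".

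SAP 5.1.3 lists DAS28-ESR with LDA and remission as yes/no variables and does not restate or rescale the cut-offs. SAP 1.6, which records departures from the protocol, covers analysis sets, a new subgroup, a baseline analysis, compliance and adverse-event coding levels. It does not mention DAS28.

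**The concern.** The appendix defines derived data as variables calculated from the CRF and not stored in the database, so its formula is the programming specification. A missing coefficient there passes into every DAS28-ESR output, while the cut-offs still come from the protocol's formula.

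The outputs affected are:

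- DAS28-ESR values and changes from baseline (secondary efficacy);
- the secondary endpoint in Protocol 9.2.1.3, "DAS28-ESR Low Disease Activity (LDA) and remission, CDAI LDA and remission, at W12 and W24", for its DAS28 half;
- the exploratory RAID and HADS mixed models (SAP 5.3.2.5), where DAS28-ESR is a covariate and would give ESR more weight than the protocol's index does;
- the patient-profile analysis (SAP 5.1.5.3), where baseline DAS28-ESR is a candidate factor.

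The two main distortions point in opposite directions: responder rates look worse, while mean improvement looks better if ESR falls on treatment. A reader could not reconcile them. In a single-arm study, results are also likely to be read against outside figures, such as the MONARCH DAS28-ESR results in Protocol 4.1.2 (remission 26.6%, mean change −3.28), and scores on another scale would not be comparable.

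**Working it through.** The documents contain no worked DAS28 value, so there is no stated figure to reproduce. The check evaluates both formulas directly.

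**Inputs.** Weight w on ln(ESR): 0.70 (Protocol 9.2.1.2) or 1.00 (SAP Appendix A). Cut-offs: <2.6 and ≤3.2 (Protocol 9.2.1.3). Stated range: 0 to 10 (Protocol 9.2.1.2). ESR is in mm/h and ln is the natural logarithm in both documents, so no unit change explains the difference.

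**Formula.** DAS28 = 0.56√TJC + 0.28√SJC + w·ln(ESR) + 0.014·PtGA.

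**Excess of SAP over protocol.** (1.00 − 0.70)·ln(ESR) = 0.30·ln(ESR):

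| ESR (mm/h) | 1 | 2 | 5 | 10 | 20 | 30 | 40 | 100 |
|---|---|---|---|---|---|---|---|---|
| Excess | 0 | 0.21 | 0.48 | 0.69 | 0.90 | 1.02 | 1.11 | 1.38 |

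**Single patients (ln 10 = 2.303).**

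- TJC 1, SJC 0, ESR 10, PtGA 20. Protocol: 0.56 + 0 + 1.612 + 0.28 = 2.45, remission. SAP: 0.56 + 0 + 2.303 + 0.28 = 3.14, not remission.
- The same patient with SJC 1 (add 0.28). Protocol: 2.73, LDA. SAP: 3.42, not LDA.

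**Highest ESR compatible with each status, with no tender or swollen joints and PtGA 0.**

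- Remission: protocol exp(2.6/0.70) = 41.0; SAP exp(2.6) = 13.5.
- LDA: protocol exp(3.2/0.70) = 96.7; SAP exp(3.2) = 24.5.

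**Stated range.** With 28 tender joints, 28 swollen joints and PtGA 100, the terms other than ESR sum to 2.963 + 1.482 + 1.4 = 5.845. The SAP score reaches 10 at ESR = exp(10 − 5.845), about 64, and is 10.45 at ESR 100. The protocol score is 9.07 at ESR 100 and reaches 10 only at an ESR of about 378.

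**Change from baseline.** The bias is 0.30·ln(ESR at visit / ESR at baseline). For an assumed fall from 35 to 8 it is 0.30·ln(8/35) = −0.44. From 40 to 8 it is −0.48. Both are spurious improvement.

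**Illustrative rates.** The documents give no Week 24 component data, so these rest wholly on assumptions: log-normal ESR (SD 0.8 on the log scale, floored at 1), negative binomial joint counts (means 4 tender and 2.5 swollen, dispersion 0.8, capped at 28), PtGA as 100 × Beta(1.3, 2.4), independent components, 400,000 draws.

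| Median ESR | Remission, protocol → SAP | LDA, protocol → SAP |
|---|---|---|
| 5 | 41.3% → 26.4% | 65.0% → 46.3% |
| 10 | 23.5% → 10.3% | 45.9% → 23.8% |
| 20 | 10.5% → 2.7% | 27.4% → 8.9% |

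A second set of assumptions (ESR centred at 8, TJC at 2.5, SJC at 1.5, PtGA at 30), tried with several distribution shapes, gave remission falling from 26% to 9% in one case and from 45% to 25% in another. LDA fell from 60% to 34% and from 71% to 44%.

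**The case against.** The discrepancy itself is hard to dispute; the objections concern its certainty and reach.

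- **Text extraction.** The text was read from PDF by a program, and a dropped coefficient cannot be wholly excluded. This is a weak objection, because the other three coefficients survived and the line reads as complete. A look at the source PDF settles it.
- **The program may be right.** The documents do not show the code. SAP 8.3 allows for code review and hand calculation, and an analyst who needs the cut-offs must go to Protocol 9.2.1.3, directly after the correct formula. Detection is therefore plausible. But SAP 8.3 also has outputs checked for consistency with the SAP, and a program using 1.00 would pass that check.
- **Size.** The simulated rates depend on invented distributions. This stands: they show a material loss under several assumptions but predict nothing for this trial. The exact result is 0.30·ln(ESR).
- **ESR of 1 or below.** The formulas agree at ESR 1, and both are undefined at 0. This stands as a limit on wording.
- **Scope.** The primary RAID endpoint, the CDAI endpoints, the sample size and the protocol's screening criterion do not use the SAP formula, and Protocol 11.4.2.3 says that all analyses are descriptive without tests. This also stands. It limits the consequences, but does not make a misclassified secondary endpoint acceptable.

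**Conclusion.** The concern holds. The SAP's DAS28-ESR formula contradicts the protocol's, the change is undeclared, and nothing in either document justifies it.

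The direction is certain: for ESR of at least 1 mm/h no patient can gain remission or LDA status through the error, and some can lose it. The size per score is exactly 0.30·ln(ESR), roughly 0.5 to 1 point for ESR between 5 and 30. That is large beside the 0.6 points separating the two cut-offs (3.2 − 2.6). The effect on the reported rates cannot be fixed from the documents.

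The conclusion assumes that the extracted line matches the source PDF and that the program follows it. It must be corrected before any DAS28-ESR result is reported.

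**What to change.** 1. Confirm the line in the source PDF, then amend SAP Appendix A, item (2), to the protocol formula: 0.56√TJC28 + 0.28√SJC28 + 0.70·ln(ESR) + 0.014·PtGA (mm). Record the correction in SAP 1.7.
2. Restate the <2.6 and ≤3.2 cut-offs beside the formula, so that score and thresholds are specified together, and state how an ESR recorded as 0 is handled.
3. Check the derivation program against the protocol formula, not only against the SAP. The first worked patient above (2.45 against 3.14) is a convenient test case.
4. Re-derive any DAS28-ESR output made with the wrong weight: values, changes, LDA, remission, the RAID and HADS association models and the profile analysis. The baseline analysis was specified in a separate SAP that is not among these documents, so check which formula it used and re-run it if affected.

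The cost is one coefficient, a program check and possibly a re-run. There is no statistical downside.
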